## **Objectives/Specific Aims**

The specific aim of the study is to evaluate the safety and efficacy of initiating earlier TR-Band weaning following transradial access procedures, while minimizing access site complications including hematoma formation and radial artery occlusion (RAO).

The primary objective is to evaluate the rate and severity of complications (i.e. hematoma, ecchymosis and radial artery occlusion) from an expedited weaning protocol wherein the time to wean is reduced significantly.

The secondary objective is to identify potential risks factors for complications following early weaning of the TR-Band.

It is hypothesized that the time to wean of the TR-Band can be safely reduced while minimizing access site complications including hematoma formation and radial artery occlusion (RAO).

## **Background**

The use of transradial (TR) access for the purpose of diagnosis and intervention in the arterial system is a well-established concept, particularly in coronary angiography, with many distinct advantages over conventional transfemoral (TF) access. The first series of 100 coronary angiographic procedures performed via TR access, published by Campeau in 1989, demonstrated 88% technical success rate and a 6% asymptomatic radial artery occlusion rate. Since then, TR access for coronary artery interventions in the United States has grown exponentially with the proportion of transradial percutaneous coronary interventions (PCI) procedures increasing from 1.2% in the first quarter of 2007 to 16.1% in the third quarter of 2012. And yet, its usage is largely absent in the interventional radiology and vascular surgery communities. Reasons for this include a lack of appropriate training and equipment, but the potential advantages of TR over TF access are abundant in both coronary and non-coronary applications. Firstly, the radial artery is more superficial than the femoral artery without surrounding neurovascular structures susceptible to injury. In addition, any sustained arterial damage is significantly less detrimental because of the hand's dual arterial vascular supply. In addition, the radial artery is readily compressible regardless of the patient's body habitus. This compressibility has been shown to decrease the incidence of post-procedural bleeding complications as well as cardiac mortality during PCI. In addition to patient safety, there are numerous benefits to overall patient comfort and convenience. For one, after TR access, patients may sit up in bed and ambulate immediately with faster discharge to home. In one randomized trial, Cooper et al demonstrated a strong patient preference, improved quality-of-life metrics, and decreased hospital costs for TR over TF access during cardiac catheterization.

Ultimately, complications with TR approach have proven rare in both coronary and noncoronary applications. Most commonly, a local small hematoma may develop with

mild pain, usually treated with NSAIDS if necessary. Despite meticulous hemostatic technique, radial artery thrombosis may occur. Nevertheless, this thrombosis almost always remains asymptomatic, at least partially because a modified Allen's test or Barbeau test is performed before all procedures using TR access. Additional possible complications of TR access include radial artery pseudoaneurysm, spasm, dissection, digit ischemia, as well as cerebral infarction, but all of the following have proven to be extremely low incidence particularly with the usage of intraprocedural heparinization and vasodilators, which are included in our procedure protocol.

Finally, and increasingly more important in the modern era of health care reform, TR access offers many benefits to hospital costs and patient satisfaction. Many studies have demonstrated decreased costs associated with TR versus traditional TF access, primarily due to the non-utilization of arterial closure devices and decreased readmission for bleeding complications. International studies have long promoted TR access as a feasible, safe, and well tolerated method for performing hepatic transarterial chemoembolization. In a recent series performed in the United States, technical success was obtained in all procedures. Furthermore, 100% of patients who underwent both TF and TR access preferred TR to TF access. Our study seeks to further establish earlier TR Band deflation as a viable and preferable method following transarterial cases to further decrease unnecessary PACU recovery time and expenses.

### **Intervention to be Studied**

TR-Band is an FDA approved device to assist achievement of hemostasis following radial access procedures. The TR-Band is not specifically FDA approved for the expedited protocol being studied here, but the standard of care FDA guidelines allow flexibility as need for the deflation protocol for each patient.

Per MUSC standard policy, after an angiographic procedure is performed via the transradial approach, hemostasis at the arterial puncture site is attained using a TR-Band (Terumo Medical Corporation, Tokyo, Japan). The TR-Band consists of a part-rigid, Velcro-secured wristband with an inflatable bladder that provides compression of the radial artery when air is injected into the cuff-valve system via the supplied syringe.

Per the Terumo guidelines, to place the TR-Band, the introducer sheath in the radial artery is first retracted 2-3 cm and the center of the compression balloon is positioned 1-2 mm proximal to the puncture site. The TR-Band is then affixed on the wrist with the adjustable Velcro fastener and 15 cc of air is injected into the cuff-valve system while simultaneously removing the introducer sheath. The amount of air in the compression balloon is subsequently titrated by removing 1 cc of air until bleeding occurs or 5 cc of air is removed. Once one of those two endpoints is met, 2 cc of air are injected into the cuff-valve system. To confirm patent hemostasis the ulnar artery at the level of the wrist is then compressed and the morphology of the plethysmographic waveform is observed – this is referred to as the reverse Barbeau's test. Absence of a plethysmographic waveform indicates interruption of antegrade radial artery flow. If this occurs, the volume

of air in the compression balloon is again titrated until the plethysmographic waveform returns.

The standard protocol is for the TR-Band to remain in place for 60 minutes. After 60 minutes, 1/4 of the total volume in the TR-Band is removed at 15-minute intervals until it is fully deflated.

The rationale for an expedited weaning protocol is based in part on the observation that after access of the femoral artery for an angiographic procedure the standard to attain hemostasis without the use of a percutaneous closure device is manual pressure at the puncture site for 15 minutes. Since the radial artery, in contradistinction to the femoral artery, is superficial and readily compressible due to the flat surface of the radius, it is counterintuitive that to attain hemostasis pressure at the radial puncture site, pressure would need to be maintained for 60 minutes. In addition, Pancholy et al concluded based on a retrospective study of 10 consecutive patients undergoing transradial coronary angiography that “shorter duration of hemostatic compression is associated with a lower incidence of early and chronic RAO, without increase in bleeding complications.”

The standard of care (control) group in the study will consist of the subset of patients wherein the time to weaning of the TR-Band is 60 minutes.

### **Study Endpoints**

The study participants will be randomly assigned into one of two groups; these groups will be defined based on the time from inflation to initiation of deflation of the TR-Band, i.e. the time to wean.

Group A (Total time about 60 minutes)	Group B (Total time about 120 minutes)
TR-Band Placed following your procedure	TR-Band Placed following your procedure
After 15 minutes deflated by 1/4	After 60 minutes deflated by 1/4
After 25 minutes deflated by 1/2	After 75 minutes deflated by 1/2
After 35 minutes deflated by 3/4	After 90 minutes deflated by 3/4
After 45 minutes deflated completely	After 105 minutes deflated completely
Observe your wrist for 15 minutes	Observe your wrist for 15 minutes
Remove TR-Band after 60 minutes	Remove TR-Band after 120 minutes

The primary outcomes will be the incidence of significant hematomas (> 5 cm in size), bleeding (continued ooze requiring re-inflation of the TR-Band or subcutaneous ecchymosis without a discernable hematoma) and occlusion of the left radial artery (based on ultrasound) at the procedure visit and at one month follow up visit

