After 35 minutes deflated by 3/4	After 90 minutes deflated by 3/4
After 45 minutes deflated completely	After 105 minutes deflated completely
Observe your wrist for 15 minutes	Observe your wrist for 15 minutes
Remove TR-Band after 60 minutes	Remove TR-Band after 120 minutes

If bleeding were to occur, the TR-Band will be re-inflated to the previous volume and the weaning protocol will be restarted after 15 minutes. Once the TR-Band is removed the patient will be re-evaluated for complications including hematoma, ecchymosis and occlusion.

Post-procedure, patients will return to the clinic 1 month following their procedure and be re-evaluated for radial access complications including hematoma, ecchymosis and occlusion; and for re-evaluation of the Barbeau test, and ultrasound.

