## **Data Management**

The data from living human subjects will include the physical examination, laboratory, and ultrasound data collected both immediately before and after the procedure; these include the pre-procedure History and Physical note, the procedure report, nursing notes and clinic Progress notes.

Only IRB approved team members will have access to the records of the patient's involved, which should be effective in controlling the confidentiality of the study. Individual, unique patient codes will be utilized in an Excel data spreadsheet for anonymization and subsequent analysis. These patient codes will be stored in a separate, secure location at the VIR Research Coordinator Office. The patient's safety will be ensured by the following methods. Prior to discharge from the PACU the patients will be given the contact information of the VIR Nurse Coordinator and clinic for any concerns. In addition, in the case of emergency, a VIR team of physicians and staff are on call at all times (24/7) to manage any acute or emergent patient issues.

The patients' characteristics (e.g. demographic information) will be compared using a t-test or chi-squared tests. The primary outcomes, i.e. rates of complications will be compared using a McNemar's test. An odds ratio will be estimated and its 95% confidence interval reported. Associations between preoperative factors and complications will be evaluated using logistic regression with random effects to account for multiple observations per patient.

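### The primary bleeding definition stops counting a bruise once a hematoma of 5 cm or less accompanies it

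*Combined protocol and SAP*

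**What the plan says.** The Study Endpoints section names three primary outcomes, assessed at the procedure visit and at one month. Two of them are given as "significant hematomas (> 5 cm in size), bleeding (continued ooze requiring re-inflation of the TR-Band or subcutaneous ecchymosis without a discernable hematoma"). The third is radial artery occlusion on ultrasound.

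Three other sections bear on the definition:

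- Objectives/Specific Aims sets the primary objective as to "evaluate the rate and severity of complications (i.e. hematoma, ecchymosis and radial artery occlusion"). It gives no size limit and no severity scale.
- Study Design/Methods has patients "re-evaluated for complications including hematoma, ecchymosis and occlusion" once the band is off, with a similar examination at one month. Neither examination has a size limit, and neither is linked to a primary-outcome category.
- Data Management says "The primary outcomes, i.e. rates of complications will be compared" and adds "An odds ratio will be estimated and its 95% confidence interval reported". It does not define complications further.

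No section says where a patient with ecchymosis and a hematoma of 5 cm or less belongs.

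**The concern.** The two restrictions do not fit together. The hematoma line begins above 5 cm, but the ecchymosis criterion is switched off by any discernible hematoma, however small. Between them lies a group that neither line picks up: a bruise with a small hematoma.

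This differs from an ordinary severity threshold. A threshold leaves mild findings uncounted. Here a finding that is already counted stops counting when a further complication, itself named in the primary objective, is added to it.

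The trial asks whether early weaning is safe. A rule that can remove injured patients from the bleeding rate matters if the removals are uneven between arms, and with at most 30 patients a few such cases would show in the reported rates.

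**Working it through.** The documents contain no figure to reproduce on this point, so the check has two parts: scoring the rule as written, and finding what one affected patient is worth.

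**1. Scoring the rule.** Inputs, all from Study Endpoints: hematoma (none, 5 cm or less, above 5 cm), ecchymosis (no, yes) and ooze needing re-inflation (no, yes), with occlusion absent. On the natural reading the restricting clause attaches to ecchymosis only. A patient is then a primary-outcome event (1) if the hematoma exceeds 5 cm, or there is ooze needing re-inflation, or there is ecchymosis with no hematoma.

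| Other findings | No hematoma | 5 cm or less | Above 5 cm |
|---|---|---|---|
| Neither | 0 | 0 | 1 |
| Ecchymosis only | 1 | **0** | 1 |
| Ooze only | 1 | 1 | 1 |
| Both | 1 | 1 | 1 |

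Each row should never fall from left to right. Only the ecchymosis row does. With occlusion added as a yes/no item there are 3 × 2 × 2 × 2 = 24 states. Among them exactly one pair has the state with more findings losing event status: ecchymosis alone against ecchymosis with a small hematoma.

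The grammar also allows the clause to govern ooze. The last three rows then all read 1, 0, 1, and there are five such pairs. The same pair fails on either reading.

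**2. Scoring the rule with the clause deleted.** Ecchymosis now counts regardless of hematoma. The ecchymosis row becomes 1, 1, 1, and no offending pair remains among the 24 states. A small hematoma with neither bruise nor ooze is still uncounted, purely because of the 5 cm threshold.

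**3. What one patient is worth.** Let an arm have n patients. Let b have ecchymosis without ooze or a large hematoma, and let m of these b also have a small hematoma. The counted bleeding rate is (b − m)/n instead of b/n, a loss of m/n.

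- The protocol gives a maximum of 30 patients and no allocation ratio. Assuming an equal split, n = 30/2 = 15, and each such patient costs 1/15 = 6.7 percentage points.
- If enrollment stops at 10 per arm (also assumed), each costs 1/10 = 10 points.

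**4. Direction.** Assume n = 15 and b = 5 in both arms. The value of b is invented for illustration. The odds ratios are unpaired, Group A versus Group B.

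| Patients with the pair (A, B) | Counted A | Counted B | Odds ratio |
|---|---|---|---|
| 1, 0 | 4/15 | 5/15 | (4/11)/(5/10) = 0.73 |
| 1, 1 | 4/15 | 4/15 | 1.00 |
| 0, 1 | 5/15 | 4/15 | (5/10)/(4/11) = 1.38 |

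With the clause deleted, all three cases give 5/15 against 5/15, odds ratio 1.00. For the first case, b = 3 gives (2/13)/(3/12) = 0.62 and b = 7 gives (6/9)/(7/8) = 0.76. The distortion always favors the arm with more bruise-plus-small-hematoma patients, and it vanishes when the arms are balanced.

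**The case against.** The best defense is that the clause prevents double counting: a patient with a hematoma belongs on the hematoma line, so ecchymosis is reserved for those without one. That would work if every discernible hematoma were counted there. Only those in "the incidence of significant hematomas (> 5 cm in size") are, so the defense fails for the smaller ones.

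A second defense is that the examinations in Study Design/Methods look for hematoma and ecchymosis at both visits without a size limit, so these patients would be noticed. That is true, and it makes this a problem of classification rather than of detection. It does not put them on a primary-outcome line.

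Other objections stand, and they limit the point:

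- A reader might infer that the Group A bleeding rate would fall as harm rises. That needs the extra small hematomas to arise in patients who would have been counted for ecchymosis anyway. If early weaning causes a bruise and a small hematoma together in a patient otherwise unharmed, the counted rate does not move; the harm is missed but not reversed. If it also causes more isolated bruising or ooze, the rate can rise.
- A reader might infer that the gap falls on the commonest complication, because Background says "Most commonly, a local small hematoma may develop with" mild pain. That sentence gives no size and does not mention ecchymosis alongside. How often the two coincide is not stated anywhere.
- A reader might infer that the endpoint contradicts the primary objective. An endpoint narrower than its objective is not in itself a contradiction, and a size threshold is one way to express severity.
- Data Management also says "Associations between preoperative factors and complications will be evaluated using logistic regression" without defining complications. That is a separate gap, which would remain with a perfect bleeding definition, and it adds no weight here.

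**Conclusion.** The point holds as a defect in the written definition. Ecchymosis with a hematoma of 5 cm or less, without re-inflation or occlusion, is counted nowhere, while the same ecchymosis alone is counted. This follows from the text on either reading of the clause. The one added premise is that a bruise with a hematoma is at least as bad as the bruise alone.

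The effect on the comparison is conditional. It arises only if these pairs are unevenly split between arms, and it understates harm from early weaning only if Group A has more of them. The documents give neither event rates nor the frequency of the combination, so the size is unknown beyond 6.7 points per affected patient at an assumed 15 per arm. The odds ratios above show direction under invented inputs. They are not estimates of likely bias, and the stronger claim that the plan will make early weaning look safer is not supported.

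**What to change.** In Study Endpoints, delete the last four words of the bleeding definition (those that limit ecchymosis to patients without a discernible hematoma). Ecchymosis then counts as bleeding whether or not a hematoma is present, and either reading of the clause is repaired. Keep the significant-hematoma line above 5 cm as it is.

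Optionally, report hematomas of 5 cm or less descriptively. Hematoma is already examined at both visits, so little extra work follows. They should not become an additional primary outcome: that would override a reasonable threshold and add a comparison to a trial of at most 30 patients.

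The costs are a small wording change, slightly higher reported bleeding rates, and the fact that a patient with ecchymosis and a hematoma above 5 cm will appear on both lines. The report should state that the lines can overlap.

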## **Number of Subjects**

The study cohort will consist of up to 30 enrolled and randomized patients age 18 years and older who undergo an angiographic procedure via the radial artery. The proposed study does not include children.

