## **Consent Process**

Once a patient is referred to Vascular and Interventional Radiology for consultation of an angiographic procedure that could be performed via the left or right radial artery, the patient will be informed of the study design by the PI, Co-I or IRB approved study team members. Some consents may be obtained prior to this during the initial consultation, but due to COVID precautions, consultations are mostly being conducted via telemedicine. We are not seeking obtain consent via tele methods. The recovery bay is great place to conduct this discussion due to privacy and that family members are often present. Patients are in prep bay for up to and over an hour prior to the procedure. The relative risks, benefits, and alternatives of the different approaches to attain hemostasis will also be discussed in detail. Informed consent will be obtained and appropriately documented in the patient's medical records. During the informed consent, it will be emphasized that regardless of the approach to hemostasis, the technical success of the intended procedure should not be affected.

The consent will be obtained at the time of the initial consultation. As stated above, no patients less than 18 years of age will be included in the study. On the day of the procedure, the design of the study and the relative risks, benefits, and alternatives of the different approaches to attain hemostasis will again be discussed in detail with the patient or patient's next of kin/medical power of attorney.

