## **Study Design/Methods**

Following approval of the methodology by IRB we will conduct a randomized, single center study of up to 30 subjects who undergo an angiographic procedure via the radial artery. Those patients who meet the inclusion criteria will be randomly assigned to one of two groups (A or B) based upon a standard randomized process using pre-designated sealed envelopes.

Pre-procedure, all patients participating in the study will be evaluated with a Barbeau test and a sonogram of the radial artery to determine the caliber of the vessel (in mm) and the distance (in mm) from anterior wall of the vessel to the skin surface. In addition, updated INR, PT and platelet count (within 14 days) and if applicable pre-procedure management of anticoagulants will be reviewed. All these variables will be documented in the TR-Band Form.

Intra-procedure, all patients participating in the study will receive conscious sedation with midazolam and fentanyl - dosage at the discretion of the operator. Once the area around the puncture site is infiltrated with less than 1 mL of 1% lidocaine, the radial artery will be cannulated with a 21-gauge needle using a modified Seldinger technique (i.e. a single wall puncture). The needle will subsequently be exchanged over a 0.021-inch wire for a hydrophilic-coated 5 Fr x 10 cm Glidesheath Slender sheath. Patients will then receive 200 micrograms of intra-arterial nitroglycerin and an initial bolus of 3000-5000 units of intra-venous heparin. Of note, patients undergoing a transradial uterine artery embolization will also receive 2.5 mg of intra-arterial verapamil. During the procedure patients will receive additional boluses of 1000 units of intra-venous heparin at 30-minute intervals. Prior to removal of the sheath, a second dose of 200 micrograms of intra-arterial nitroglycerin will be administered and an ACT value will be measured. After the sheath is removed, hemostasis will be attained with a TR-Band. The TR-Band consists of a part-rigid, Velcro-secured wristband with an inflatable bladder that provides compression of the radial artery when air is injected into the cuff-valve system via the supplied syringe.

Group A (Total time about 60 minutes)	Group B (Total time about 120 minutes)
TR-Band Placed following your procedure	TR-Band Placed following your procedure
After 15 minutes deflated by 1/4	After 60 minutes deflated by 1/4
After 25 minutes deflated by 1/2	After 75 minutes deflated by 1/2

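### The primary occlusion outcome is tied to the left radial artery, although the protocol allows access from either side

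*Combined protocol and SAP*

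**What the plan says.** The primary outcomes in Study Endpoints are significant hematoma, bleeding, and "occlusion of the left radial artery (based on ultrasound) at the procedure visit and at one month follow up visit". Only the occlusion outcome names a side.

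Elsewhere the side is open or follows the access:

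- Consent Process describes patients referred for "an angiographic procedure that could be performed via the left or right radial artery".
- Number of Subjects plans for "up to 30 enrolled and randomized patients age 18 years and older who undergo an angiographic procedure via the radial artery", and Study Design/Methods for "a randomized, single center study of up to 30 subjects who undergo an angiographic procedure via the radial artery". Neither gives a side.
- Objectives/Specific Aims treats radial artery occlusion as a complication of the access site.
- Study Design/Methods states "Once the TR-Band is removed the patient will be re-evaluated for complications including hematoma, ecchymosis and occlusion", and at one month patients are "re-evaluated for radial access complications including hematoma, ecchymosis and occlusion".
- Risks to Subjects plans the pre-procedure sonogram on the artery that is to be accessed.

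The eligibility section is mixed. The Barbeau test is done on the limb to be used. The inclusion criterion of at least 1.6 mm names no side, but the matching exclusion (less than 1.6 mm) names the left artery.

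**The concern.** The TR-Band compresses the puncture site, so weaning time can affect only the artery that was accessed. In a right-access patient the left artery carries no information about the intervention. Applied literally, the definition records such a patient as free of occlusion whatever happened at the access site.

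Occlusion is one of three primary outcomes and is named in the study aim and hypothesis. Losing occlusions would lower the recorded rate in both groups and thin out a count that is already small in at most 30 patients. If assessors are left to infer the side, some may follow the definition and others the accessed artery, and scoring would be inconsistent.

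The exclusion criterion raises the same difficulty. Read literally, it could exclude a right-access candidate because of an artery that will not be used and that the planned sonogram would not cover.

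**Working it through.** **Reading the text.** Nothing in the protocol says that left, in the outcome definition, stands for the accessed side, and no eligibility rule requires left access. Two readings are possible.

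1. Either side may be used. Then the outcome definition and the diameter exclusion are wrong for right-access patients.
2. Only left access is intended. Then both are right, but the Consent Process wording is wrong and the population descriptions omit a restriction.

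The text needs correcting under either reading.

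**Size if the literal definition is applied.** The plan states no occlusion rate or right-access share for its design, so there is no figure of its own to reproduce. The inputs are:

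- N = 30, the enrolment ceiling (Number of Subjects).
- p = 6%, for illustration only, from the early coronary series cited in Background.
- r = right-access share, not given and possibly zero; taken as 10%, 25% and 50%.
- Assumptions: r is equal in both groups, the risk is the same on either side, and no occlusion occurs in an uncannulated artery.

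The recorded rate is then p(1 − r). The formulas are:

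- Expected access-site occlusions: 30 × 0.06 = 1.8.
- Unrecorded: 1.8 × r.
- Chance that none is recorded: (1 − 0.06(1 − r))^30.

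| r | Recorded | Unrecorded | Chance that none is recorded |
|---|---|---|---|
| 0 | 1.80 | 0 | 0.94^30 = 15.6% |
| 10% | 1.62 | 0.18 | 0.946^30 = 18.9% |
| 25% | 1.35 | 0.45 | 0.955^30 = 25.1% |
| 50% | 0.90 | 0.90 | 0.97^30 = 40.1% |

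Data Management says "An odds ratio will be estimated and its 95% confidence interval reported". With no recorded occlusion in either group, that ratio cannot be estimated for occlusion on its own.

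**Comparison between groups.** Take assumed true rates of 12% and 6%, each multiplied by (1 − r). The risk ratio is 12(1 − r) / 6(1 − r) = 2.0 for every r. The odds ratio is:

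- r = 0: (0.12/0.88) / (0.06/0.94) = 2.14
- r = 10%: (0.108/0.892) / (0.054/0.946) = 2.12
- r = 25%: (0.09/0.91) / (0.045/0.955) = 2.10
- r = 50%: (0.06/0.94) / (0.03/0.97) = 2.06

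If the true rates are equal, both ratios stay at 1.0. The loss is therefore in event count and in the absolute rate, with almost no change in the relative comparison.

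**The case against.** The strongest reply is that this is a slip of wording with no practical effect. Harm needs two things together: right-access patients are enrolled, and staff then scan an artery that was never punctured. Apart from the definition itself, nothing directs such a scan, and the assessment text points to the access site. That stands as a limit on the likely impact. It does not make the definition right, because assessors and analysts should be able to follow a primary outcome as written.

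Right access also rests on one clause in the consent section, while left appears in both the outcome and the exclusion, so a left-only trial is a live reading. That is fair, but it still conflicts with the Consent Process text.

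Sparse data come mainly from the sample size. Assuming 15 per group and 6% in both, the chance that at least one group has no occlusion, which leaves the ordinary odds ratio zero, infinite or undefined, is 1 − (1 − 0.94^15)² = 63% with r = 0. Replacing 0.94 by 1 − 0.06(1 − r) gives 68%, 75% and 87% for r = 10%, 25% and 50%. This stands: at a modest right-access share the wording adds little to a problem that is already there. The plan also ties the odds ratio to complication rates and does not say that occlusion will be analysed alone.

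Two smaller points also carry weight. If the left artery of a right-access candidate is never scanned, the left-only exclusion cannot operate in practice, so it is the same slip repeated. And "All these variables will be documented in the TR-Band Form" refers to pre-procedure measurements; it is not a full list of trial data, so the absence of access side there does not prove that it goes unrecorded. The procedure report, a named data source, may show it.

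**Conclusion.** The concern holds. The outcome definition contradicts the access allowed in Consent Process and does not match the access-site language in the aims, assessments and risks. Followed as written, it would miss every access-site occlusion in right-access patients.

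The contradiction is certain; its effect on the results is not. The effect is nil if the accessed artery is scored or no right access occurs. Otherwise the fraction of occlusions lost equals the right-access share: up to 0.90 of 1.8 expected events over the range examined, under the illustrative 6% rate and the assumptions listed. Because patients are randomized, neither group is expected to be favoured. Hematoma and bleeding are not affected. It should be fixed because it concerns a primary outcome and the correction costs almost nothing.

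**What to change.** In Study Endpoints, define the outcome as occlusion, by ultrasound, of the accessed radial artery, meaning the one to which the TR-Band was applied. Reconcile the left-only diameter exclusion with the unsided inclusion criterion beside it, and with Consent Process and Risks to Subjects. Confirm that access side is captured for every patient, either on the TR-Band Form or from the procedure report.

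If only left access is intended, leave the outcome as it is and say so in Number of Subjects, Consent Process and Study Design/Methods.

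Either route is a few words in two or three sections. The ultrasound is already planned, so no extra visits, procedures or patients are needed.
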